11.8.11. Pharmacodynamic Figures

Pharmacodynamic (and or Biomarker) : Figures					
No.	Population	IDSL / TST ID / Example Shell	Title	Programming Notes	Deliverable [Priority]
IFN mRNA signature					
5.1.	Safety	PD_F1	Individual Subject Profiles for mRNA Expression of IFN Signatures in Skin Biopsies (Group B-Natural Lesions)	Symbol by subject id, column panel by treatment group (Placebo and GSK2646264) Symbol by subject Id. Line pattern by CLE type See Section 11.3.5 for list of genes and probe-sets to be summarised	SAC
5.2.	Safety	PD_F3	Adjusted Mean Intensities (95% CI) for mRNA Expression IFN Signatures in Skin Biopsies (Group B-Natural Lesions)	Y xais – log2 scale By treatment group (Placebo and GSK2646264) Jitter by treatment (i.e. do not overlay the mean error bars.)	SAC
5.3.	Safety	PD_F4	Adjusted Mean (95% CI) Fold Change in mRNA Expression of IFN Signatures in Skin Biopsies (Group B-Natural Lesions)	Page by Gene ID. X-axis - probeset ID Include band from FC -1 to 1, transparency 0.5 Footnote: 'Comparison to placebo' is the fold change on GSK2646264 relative to placebo in log ₂ intensity at day 28.'	SAC
5.4.	Safety	PD_F5	Individual Plot of mRNA Expression of IFN Signatures in Skin Biopsies by Skin Type (Group B-Natural Lesions)	Symbol by CLE type, column panel by skin type. X-axis – subject id Symbol by CLE type See Section 11.3.5 for list of genes and probe-sets to be summarised	SAC

Pharmacodynamic (and or Biomarker) : Figures					
No.	Population	IDSL / TST ID / Example Shell	Title	Programming Notes	Deliverable [Priority]
5.5.	Safety	PD_F6	Adjusted Mean Intensities (95% CI) for mRNA Expression IFN Signatures in Skin Biopsies (Group B-Natural Lesions)	Since only one timepoint, replace x-axis with skin type. Symbol by subject Id. Include individual raw values	SAC
5.6.	Safety	PD_F6	Adjusted Mean (95% CI) Fold Change in mRNA Expression of IFN Signatures in Skin Biopsies by Skin Type (Group B-Natural Lesions)	Page by Gene ID. X-axis - probeset ID By Skin Type – symbol by skin type Include band from FC -1 to 1, transparency 0.5 Footnote: 'Comparison to uninvolved' is the fold change on GSK2646264 relative to placebo in \log_2 intensity.'	SAC
Exploratory PD endpoints					
5.7.	Safety	PD_F1	Individual plot of cell markers from Immunohistochemistry (Group B-Natural Lesions)	Symbol by subject id, column panel by treatment group (Placebo and GSK2646264) Symbol by subject Id. Line pattern by CLE type Heading: [marker name and description]	SAC
5.8.	Safety	Similar to PD_F2	Plot of Mean and SE of cell markers from Immunohistochemistry (Group B-Natural Lesions)	By treatment group (Placebo and GSK2646264) Panel by CLE type (include All). Heading: [marker name and description]	SAC

Pharmacodynamic (and or Biomarker) : Figures					
No.	Population	IDSL / TST ID / Example Shell	Title	Programming Notes	Deliverable [Priority]
5.9.	Safety	PD_F6	Plot of Mean and SE of cell markers from Immunohistochemistry by Skin Type(Group B-Natural Lesions)	Since only one timepoint, replace x-axis with skin type. Include individual raw values Symbol by subject Id. Panel by CLE type (include All) Heading: [marker name and description]	SAC
5.10.	Safety	PD_F1	Individual plot of Histopathology score and components in skin biopsies (Group B-Natural Lesions)	Symbol by subject id, column panel by treatment group (Placebo and GSK2646264) Symbol by subject Id. Line pattern by CLE type	SAC
5.11.	Safety	Similar to PD_F2	Plot of Mean and SE in Histopathology score and components in skin biopsies (Group B-Natural Lesions)	By treatment group (Placebo and GSK2646264) Panel by CLE type (include All)	SAC
5.12.	Safety	PD_F6	Plot of Mean and SE in Histopathology score and components in skin biopsies by skin type (Group B-Natural Lesions)	Since only one timepoint, replace x-axis with skin type Include individual raw values Symbol by subject Id. Panel by CLE type (include All) Heading: [type of score]	SAC

11.8.12. ICH Listings

ICH : Listings					
No.	Population	IDSL / TST ID / Example Shell	Title	Programming Notes	Deliverable [Priority]
Subject Disposition					
1.	PV Failures	ES7	Listing of Reasons for Screen Failure (Group A- PV lesions)		SAC
2.	All Screened	ES7	Listing of Reasons for Screen Failure (Group B-Natural Lesions)		SAC
3.	Safety	ES2	Listing of Reasons for Study Withdrawal (Group B-Natural Lesions)		SAC
4.	Safety	BL1 / BL2	Listing of Subjects for Whom the Treatment Blind was Broken (Group B-Natural Lesions)		SAC
5.	Safety	CP_RD1x	Listing of Planned and Actual Treatments (Group B-Natural Lesions)		SAC
Protocol Deviations					
6.	Safety	DV2	Listing of Important Protocol Deviations (Group B-Natural Lesions)		SAC
7.	Safety	IE3	Listing of Subjects with Inclusion/Exclusion Criteria Deviations (Group B-Natural Lesions)		SAC
Populations Analysed					
8.	All Screened	SA3a	Listing of Subjects Excluded from Any Population (Group B-Natural Lesions)		SAC
Demographic and Baseline Characteristics					
9.	Safety	DM2	Listing of Demographic Characteristics (Group B-Natural Lesions)	Include BMI	SAC
10.	Safety	DM9	Listing of Race (Group B-Natural Lesions)		SAC

ICH : Listings					
No.	Population	IDSL / TST ID / Example Shell	Title	Programming Notes	Deliverable [Priority]
Medical History					
11.	Safety	MH2	Listing of Medical History (Group B-Natural Lesions)		SAC
Prior and Concomitant Medications					
12.	Safety	CP_CM3	Listing of Concomitant Medications (Group B-Natural Lesions)		SAC
Exposure and Treatment Compliance					
13.	Safety	EX3	Listing of Weight of Study Cream Applied (Group B-Natural Lesions)	If applicable adapt to study data See Section 11.3.2 regarding total daily dose of cream i.e. each subject to have one row per day, with weight of cream listed (the total weight calculated from the weight before and after application), column labelled as "Weight of Cream (g)" and each body location/side listed together on that single row.	SAC
Adverse Events					
14.	Safety	CP_AE8	Listing of All Adverse Events (Group B-Natural Lesions)	No treatment heading.	SAC
15.	PV failures	CP_AE8	Listing of All Adverse Events for subjects that were PV failures (Group A-PV Lesions)	No treatment heading.	SAC
16.	Safety	AE7	Listing of Subject Numbers for Individual Adverse Events (Group B-Natural Lesions)	Treatment column will not be displayed.	SAC
17.	Safety	AE2	Listing of Relationship Between Adverse Event System Organ Classes, Preferred Terms, and Verbatim Text (Group B-Natural Lesions)		SAC

CONFIDENTIAL

204860

ICH : Listings					
No.	Population	IDSL / TST ID / Example Shell	Title	Programming Notes	Deliverable [Priority]
Serious and Other Significant Adverse Events					
18.	Safety	CP_AE8a	Listing of Serious Adverse Events (Group B-Natural Lesions)	No treatment heading.	SAC
19.	Safety	AE14	Listing of Reasons for Considering as a Serious Adverse Event (Group B-Natural Lesions)		SAC
20.	Safety	CP_AE8	Listing of Adverse Events Leading to Withdrawal from Study / Permanent Discontinuation of Study Treatment (Group B-Natural Lesions)	No treatment heading.	SAC
Hepatobiliary (Liver)					
21.	Safety	MH2	Listing of Medical Conditions for Subjects with Liver Stopping Events (Group B-Natural Lesions)	Treatment column will not be displayed	SAC
22.	Safety	SU2	Listing of Substance Use for Subjects with Liver Stopping Events (Group B-Natural Lesions)	Treatment column will not be displayed	SAC
All Laboratory					
23.	Safety	LB5	Listing of Laboratory Data for Subjects with Abnormalities of Potential Clinical Concern (Group B-Natural Lesions)	No treatment heading.	SAC
24.	Safety	LB5	Listing of Laboratory Data for Subjects with Abnormalities of Potential Clinical Concern-Change from Baseline (Group B-Natural Lesions)	No treatment heading.	SAC
25.	Safety	LB5	Listing of Laboratory Data Abnormalities of Potential Clinical Importance (Group B-Natural Lesions)	No treatment heading.	SAC
26.	Safety	LB5	Listing of Laboratory Data Abnormalities of Potential Clinical Importance- change from baseline (Group B-Natural Lesions)	No treatment heading.	SAC

ICH : Listings					
No.	Population	IDSL / TST ID / Example Shell	Title	Programming Notes	Deliverable [Priority]
ECG					
27.	Safety	CP_EG3	Listing of All ECG Values for Subjects with a Value of Potential Clinical Importance (Group B-Natural Lesions)	No treatment heading.	SAC
28.	Safety	CP_EG3	Listing of ECG Values of Potential Clinical Importance (Group B-Natural Lesions)	No treatment heading.	SAC
29.	Safety	CP_EG3	Listing of All ECG Values for Subjects with a Value of Potential Clinical Importance- Change from Baseline (Group B-Natural Lesions)	No treatment heading.	SAC
30.	Safety	CP_EG3	Listing of ECG Values of Potential Clinical Importance-Change from Baseline (Group B-Natural Lesions)	No treatment heading.	SAC
31.	Safety	CP_EG5	Listing of Abnormal ECG Findings (Group B-Natural Lesions)	No treatment heading.	SAC
Vital Signs					
32.	Safety	CP_VS4	Listing of All Vital Signs for Subjects with Values of Potential Clinical Importance (Group B-Natural Lesions)	Treatment column will not be displayed	SAC
33.	Safety	CP_VS4	Listing of All Vital Signs for Subjects with Values of Potential Clinical Importance –Change from baseline (Group B-Natural Lesions)	Treatment column will not be displayed	SAC

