### 5.3. Screening/Baseline Failures

Screen failures are defined as subjects who consent to participate in the clinical trial but are never subsequently randomised. In order to ensure transparent reporting of screen failure subjects, meet the Consolidated Standards of Reporting Trials (CONSORT) publishing requirements, and respond to queries from Regulatory authorities, a minimal set of screen failure information is required including Demography, Screen Failure details, Eligibility Criteria, and Serious Adverse Events (see Section 7.4.1.6).

Screening assessments that yield initially aberrant results (e.g. safety laboratory samples) may be repeated by the investigator based on their judgement. Subject re-screening is allowed up to a maximum of 2 times.

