#### **7.4.1.1. Time period and Frequency for collecting AE and SAE information**

- Any SAEs assessed as related to study participation (e.g., protocol-mandated procedures, invasive tests, or change in existing therapy) or related to a GSK product will be recorded from the time a subject consents to participate in the study up to and including any follow-up contact.

- AEs will be collected from the start of Study Treatment until the follow-up contact (see Section 7.4.1.3), at the timepoints specified in the Time and Events Table (Section 7.1).
- Medical occurrences that begin prior to the start of study treatment but after obtaining informed consent may be recorded on the Medical History/Current Medical Conditions section of the CRF.
- All SAEs will be recorded and reported to GSK within 24 hours, as indicated in Section 12.3 Appendix 3.
- Investigators are not obligated to actively seek AEs or SAEs in former study subjects. However, if the investigator learns of any SAE, including a death, at any time after a subject has been discharged from the study, and he/she considers the event reasonably related to the study treatment or study participation, the investigator must promptly notify GSK.

NOTE: The method of recording, evaluating and assessing causality of AEs and SAEs plus procedures for completing and transmitting SAE reports to GSK are provided in [Appendix 4](#).

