4. ANALYSIS POPULATIONS

Population	Definition / Criteria	Analyses Evaluated
Safety	
 • Comprise of all subjects who receive at least one dose of study treatment. • This population will be based on the treatment the subject actually received. 	
 • Study Population • Safety • Efficacy • Pharmacodynamic
Pharmacokinetic	
 • Subjects in the 'Safety' population for whom a pharmacokinetic sample was obtained and analysed. 	
 • PK
PV Failures	
 • Subjects who enrolled into Group A but were not randomised to a treatment. 	
 • AEs relating to PV • Concomitant medications
All Screened	
 • Comprises of all subjects who have entered the study 	
 • Screen failures

NOTES :

- Please refer to [Appendix 8](#): List of Data Displays which details the population to be used for each display being generated.

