7. PRIMARY STATISTICAL ANALYSES

7.1. Safety Analyses

7.1.1. Overview of Planned Adverse Events Analyses

The safety analyses will be based on the Safety population, unless otherwise specified.

Table 3 provides an overview of the planned analyses, with full details of data displays being presented in [Appendix 8: List of Data Displays](#).

Table 3 Overview of Planned Adverse Events Analyses

Endpoint / Parameter/ Display Type	Absolute		
	Summary		Individual
	T	F	L
Adverse Events (AEs)			
All AEs by SOC	Y		Y
All Drug-Related AEs by SOC	Y		
Subject Numbers for Individual AEs			Y
Relationship Between AE SOCs, PT & Verbatim Text			Y
Serious and Other Significant AEs			
Non-Fatal Serious AEs			Y
Serious AEs by SOC	Y		
Reasons for Considering as a Serious AE			Y
AEs Leading to Withdrawal from Study / Permanent Discontinuation of Study Treatment by Overall Frequency	Y		Y

[1] Plot of common AEs and relative risk will be generated.

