11.8.5. Safety Tables

Safety : Tables					
No.	Population	IDSL / TST ID / Example Shell	Title	Programming Notes	Deliverable [Priority]
Adverse Events					
2.1.	Safety	CP_AE1p	Summary of All Adverse Events by System Organ Class (Group B-Natural Lesions)	Only Total adverse events will be summarised.	SAC
2.2.	Safety	CP_AE1p	Summary All Drug-Related Adverse Events by System Organ Class (Group B-Natural Lesions)	Only Total adverse events will be summarised.	SAC

Safety : Tables					
No.	Population	IDSL / TST ID / Example Shell	Title	Programming Notes	Deliverable [Priority]
Serious and Other Significant Adverse Events					
2.3.	Safety	CP_AE1p	Summary of Serious Adverse Events by System Organ Class (Group B-Natural Lesions)	Only Total adverse events will be summarised.	SAC
2.4.	Safety	CP_AE1p	Summary of Adverse Events Leading to Withdrawal from Study / Permanent Discontinuation of Study Treatment by Overall Frequency (Group B-Natural Lesions)	Only Total adverse events will be summarised.	SAC
Laboratory: Chemistry					
2.5.	Safety	LB1	Summary of Chemistry Changes from Baseline (Group B-Natural Lesions)	Treatment column will not be displayed.	SAC
2.6.	Safety	LB3	Summary of Emergent Chemistry Results Relative to Normal Range (Group B-Natural Lesions)	Treatment columns will be replaced by one 'Part B' column	SAC
Laboratory: Hematology					
2.7.	Safety	LB1	Summary of Hematology Changes from Baseline (Group B-Natural Lesions)	Includes baseline values. Treatment column will not be displayed.	SAC
2.8.	Safety	LB3	Summary of Emergent Hematology Results Relative to Normal Range (Group B-Natural Lesions)	As notes for Chemistry T2.12.	SAC
Laboratory: Urinalysis					
2.9.	Safety	LB1	Summary of Urine Concentration Changes from Baseline (Group B-Natural Lesions)	Includes Baseline values. Treatment column will not be displayed.	SAC
2.10.	Safety	LB2	Summary of Emergent Urinalysis Dipstick Results (Group B-Natural Lesions)	As above for Chemistry, using dipstick categories.	SAC
Laboratory: Hepatobiliary (Liver)					
2.11.	Safety	LIVER1	Summary of Liver Monitoring/Stopping Event Reporting (Group B-Natural Lesions)	Treatment columns will be replaced by one 'Part B' column	SAC

Safety : Tables					
No.	Population	IDSL / TST ID / Example Shell	Title	Programming Notes	Deliverable [Priority]
2.12.	Safety	LIVER10	Summary of Subjects Meeting Emergent Hepatobiliary Laboratory Abnormality Criteria (Group B-Natural Lesions)	Treatment columns will be replaced by one 'Part B' column	SAC

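### No planned SAP table or listing would show a serious adverse event in a Group B subject who was never dosed

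*SAP*

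**What the plan says.** Collection. Protocol 7.4.1.1 covers "Any SAEs assessed as related to study participation (e.g., protocol-mandated procedures, invasive tests, or change in existing therapy" as well as those related to a sponsor product, and says that they "will be recorded from the time a subject consents to participate in the study up to and including any follow-up contact". Non-serious adverse events are collected only from the start of study treatment.

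Screen failures. Under protocol 5.3 a consented subject who is never randomised is a screen failure. For transparent reporting of these subjects, "a minimal set of screen failure information is required including Demography, Screen Failure details, Eligibility Criteria, and Serious Adverse Events". The Analysis paragraph of the protocol synopsis adds a general commitment to list and summarise all data.

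Reporting. SAP 7.1.1 sets the default: "The safety analyses will be based on the Safety population, unless otherwise specified". SAP section 4 defines that population: "Comprise of all subjects who receive at least one dose of study treatment". In SAP 11.8.5 and 11.8.12 the population column reads Safety for Table 2.3 ("Summary of Serious Adverse Events by System Organ Class (Group B-Natural Lesions"), for Listing 18 ("Listing of Serious Adverse Events (Group B-Natural Lesions") and for Listing 19 ("Listing of Reasons for Considering as a Serious Adverse Event (Group B-Natural Lesions"). One adverse event display covers undosed subjects: Listing 15, for Group A subjects who were enrolled but not randomised.

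**The concern.** The SAE collection window opens at consent, but the SAE displays admit only subjects who reached a first dose. In Group B the interval between those two points contains an invasive procedure, namely three punch biopsies. Whether a subject enters the Safety population may also depend on the event: a serious complication at a biopsy site could be the reason a subject does not go on to Day 1. That is an inference about how the gap could arise. The documents do not describe a case.

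At stake is the completeness of the SAE listing in a study whose primary objective is safety and tolerability, in the only group that had randomised subjects (SAP 2.1) and with about 15 subjects planned. In a group of that size each serious event is read individually, so the listing carries more weight than any summary.

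**Working it through.** The plan states no figure on this point, so the check is a trace from collection to display.

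1. When can a relevant SAE arise? From consent (protocol 7.4.1.1). In Group B, lesions F and G and uninvolved area H are biopsied at Day -5 to -3 (protocol 4.1 and 7.6.1). Randomisation and first dose follow after 2 to 4 days of healing (protocol 7.1.3).
2. Can a subject be biopsied and then not dosed? Yes. Safety laboratory samples, a pregnancy test, an ECG and a brief physical examination are all scheduled pre-dose on Day 1, and a subject may withdraw at any time. A subject never randomised is a screen failure. A subject randomised but never dosed is also possible: SAP 11.3.2 provides for randomised subjects with no treatment start date.
3. Is either kind of subject in the Safety population? No, because neither has received a dose.
4. Which displays could show the event? Taking every adverse event and population display in SAP 11.8.4, 11.8.5 and 11.8.12 that covers Group B, plus Listing 15:

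| Display | Population | Shows an SAE in an undosed Group B subject? |
|---|---|---|
| Table 2.3, Listings 18 and 19 (SAEs) | Safety | No |
| Tables 2.1, 2.2, 2.4; Listings 14, 16, 17, 20 (other adverse event displays) | Safety | No |
| Listing 15 (adverse events) | PV Failures, Group A only | No |
| Table 1.3, Listing 2 (reasons for screen failure) | All Screened | No, reason only |
| Table 1.7, Listing 8 (populations and exclusions) | All Screened | No, membership only |

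5. Count. Group B SAE displays on the Safety population: 3 of 3. All Group B adverse event displays on the Safety population: 3 + 7 = 10 of 10. Group B adverse event displays on any population that includes undosed subjects: 0. Group A has one, Listing 15.
6. Does an exception apply? SAP 7.1.1 allows for another population to be specified, but none is specified for these displays.
7. Is it a declared change? SAP 2.1 lists the clarified PK endpoint, the absence of randomised Group A subjects with listings for the photoprovocation failures, and the dropping of formal RCLASI analysis. It says nothing about SAEs in undosed Group B subjects.

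**The case against.** The best defence is that the event is not lost. Protocol 7.4.1.1 requires SAEs to reach the sponsor within 24 hours, 7.4.1.6 covers regulatory and ethics notification, and 10.8 has the Safety Review Team reviewing SAEs in-stream. This stands. A reader might infer that such an SAE would be reported nowhere, and the documents do not support that. The gap is confined to the SAP's planned displays.

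A reader might also infer that the report would understate a count of procedure-related SAEs. No planned output gives such a count: Table 2.3 counts all SAEs by system organ class and Table 2.2 counts drug-related events. An undosed subject says nothing about the toxicity of the cream, so the Safety population is right for those tables.

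Protocol 5.3 points its SAE item to the section on regulatory reporting and does not prescribe a listing. That weakens 5.3 as a source taken alone. However, its stated purpose includes transparent reporting of screen failures, and the synopsis commitment to list all data carries no such qualification.

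Finally, Listing 15 has a reason of its own. No Group A subject was randomised, so without it Group A would have no adverse event output. That explains why the SAP provides it, but not why Group B, with its own invasive pre-dose procedure, has no counterpart.

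**Conclusion.** The point holds as a narrow omission in the planned displays, of low severity. A participation-related SAE in a Group B subject who never received a dose is collected under the protocol but cannot appear in any SAP table or listing. This follows directly from the population definitions and needs no assumption. It conflicts with the protocol's purpose for screen-failure data and with its commitment to list all data, and it is undeclared.

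Its practical size cannot be stated. An event is omitted only if a subject consents, is not dosed and has a recordable SAE. The documents give neither the fraction of biopsied subjects who are not dosed nor an SAE rate after biopsy. Assuming a non-dosing fraction and applying it to the planned 15 subjects would count undosed subjects, not missed SAEs, so it would not measure the gap. The number of events may be zero. Nothing here bears on dosing, stopping or other patient care.

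**What to change.** Either of two changes closes the gap:

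- Set the population of Listings 18 and 19 to All Screened and add a dosed/not-dosed flag.
- Add one Group B SAE listing for screened-but-undosed subjects, parallel to Listing 15. It should include anyone randomised but never dosed.

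In both cases show the event date and the biopsy date for undosed subjects. SAP 11.3.1 anchors study day to the randomisation date, which a never-randomised subject does not have. Keep Tables 2.1 to 2.4 on the Safety population, and state the exception in SAP 7.1.1.

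The cost is minor programming and possibly an empty listing, which would itself document that no such event was recorded. No new data are needed: SAEs are recorded from consent, protocol 7.5.2 records the biopsy date, and Listing 2 already assigns screen failures to Group B.

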11.8.13. Non-ICH Listings

Non-ICH : Listings					
No.	Population	IDSL / TST ID / Example Shell	Title	Programming Notes	Deliverable [Priority]
Study Population					
34.	Safety	SAFE_L2	Listing of Type of CLE (Group B-Natural Lesions)	Obtained from medical conditions page in eCRF. Under Disease Diagnosis – 2. Disease characteristics.	
Local tolerability					
35.	Safety	SAFE_L1	Listing of local tolerability (Group B-Natural Lesions)	Include maximal dermal response	SAC
RCLASI					
36.	Safety	PD_L1	Listing of RCLASI and components (Group B-Natural Lesions)	Include change from baseline. Include a footnote to explain the derivation	SAC

Non-ICH : Listings					
No.	Population	IDSL / TST ID / Example Shell	Title	Programming Notes	Deliverable [Priority]
Pharmacokinetic					
37.	PK	PKCI1P	Listing of Plasma GSK2646264 Pharmacokinetic Concentration-Time Data (Group B-Natural Lesions)		SAC
38.	PK	PKPL1P	Listing of Derived Plasma GSK2646264 Pharmacokinetic Parameters (Group B-Natural Lesions)		SAC
Pharmacodynamic					
39.	Safety	PD_L2	Listing of transcriptomic mRNA expression in skin biopsies for selected probesets (Group B-Natural Lesions)	See Section 11.3.5 for list of genes and probe-sets to be listed	SAC
40.	Safety		Raw SAS output from the statistical analysis of change from baseline IFN proteins in skin biopsies (Group B-Natural Lesions)		SAC
41.	Safety		Raw SAS output from the statistical analysis of IFN proteins in skin biopsies by skin type (Group B-Natural Lesions)		SAC
42.	Safety	PD10	Listing of Cell Markers from Immunohistochemistry (Group B-Natural Lesions)	Include change from baseline	SAC
43.	Safety	PD_L3	Listing of Histopathology score and components in skin biopsies (Group B-Natural Lesions)	Include change from baseline. Column for Skin Area (e.g. F, G and H). Each subject has two forms. Thus listing will include both values.	SAC
44.	Safety	PD_L4	Listing of QC criteria from Histological scoring form (Group B-Natural Lesions)	This will include listing of QC Criteria section of the form.	SAC

